Transfer from Part A to Part B: Since Part A will be the first time patients in intensive care are receiving ETX2514SUL, PK in the first approximately 30 patients must be verified prior to initiating Part B to ensure the treatment planned in Part B is optimal for the targeted patient population. Patients randomized to either group of Part A can only be transferred to Part B, once Part B is open for enrollment, if the ABC identified from the baseline culture is subsequently determined to be resistant to colistin or polymyxin B by the local microbiology laboratory. If Part B is not yet open for enrollment in a given country and a patient in Part A has a baseline culture determined to be colistin- or polymyxin B-resistant but is responding to therapy, the patient may remain in Part A at the discretion of the Investigator. A patient in Part A whose culture is determined to be colistin or polymyxin B-resistant and who has not shown improvement or whose condition has worsened will be withdrawn from the study drug treatment. All such cases must be discussed with the Medical Monitor.

Any organism isolated from the blood or infection site-specific cultures will be identified by genus and species by the local laboratory. Organisms will be cultured and quantified (urine and bronchoalveolar lavage only) at the local laboratory, and susceptibility of the organism(s) will be performed per local laboratory standards. Isolates of pathogens cultured at the local laboratory are to be sent to the central laboratory for confirmation of identification and susceptibility testing.

No dosing regimen changes, other than those specified in the protocol for renal insufficiency or for patients on imipenem who develop a seizure that is thought to be directly related to imipenem, can occur without discussion with the Medical Monitor. Patients with cultures growing organisms

[figure not shown]

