with evidence of carbapenem resistance should remain on their assigned treatment regimen; treatment regimen changes can occur after 5 days after discussion with the Medical Monitor. If changes to the regimen are needed due to unsatisfactory clinical response, patients should be classified as clinical failures and discontinued from study drug. All patients should receive at least 48 hours of IV study drug (ie, 8 doses of ETX2514SUL plus 8 doses of imipenem/cilastatin or 4 doses of colistin plus 8 doses of imipenem/cilastatin in patients without dose adjustments) before the Investigator considers the patient to be a clinical failure and discontinues the patient from study drug therapy.

Note: Patients who experience focal tremors, myoclonus, or seizures at any point during the study should be evaluated neurologically, placed on anticonvulsant therapy (if not already instituted), and the dose of imipenem/cilastatin should be evaluated to determine whether it should be decreased or discontinued.

Day 1 is defined as the first day of study drug administration. The subsequent study days are defined by the number of treatment days thereafter. Treatment days should constitute 24 hours of treatment. For those patients with no dose adjustments, the duration of antibiotic treatment with study drug therapy will be 28 doses of ETX2514SUL plus 28 doses of imipenem/cilastatin or 14 doses of colistin plus 28 doses of imipenem/cilastatin (ie, treatment for 7 days for those without dose adjustments), with a prolongation of therapy up to 14 days if clinically indicated. Refer to the Pharmacy Manual for specifics on dosing for all patients.

The overall study design is shown in the figure below.

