#### **9.1.3. Baseline Definition**

For microbiological data, baseline pathogen(s) are determined from the specimens collected prior to the first dose of study drug.

For all efficacy and safety endpoints, baseline is defined as the last measurement or assessment prior to the first dose of study drug.

For safety endpoints, patients who were randomized into Part A then transferred into Part B will be included in both Part A and Part B, baseline is defined as the last measurement or assessment prior to the first dose of study drug of Part A for both Part A and Part B safety analysis.

For efficacy endpoints, patients who were randomized into Part A then transferred into Part B will be included in Part B only, baseline is defined as the last measurement or assessment prior to the first dose of study drug of Part A for Part B efficacy analysis.

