### **9.3. Efficacy Analyses**

The efficacy analyses will be analyzed for Part A and Part B separately. Patients who were randomized into Part A and stayed in Part A will be summarized/analyzed only for Part A. Patients who were randomized into Part A but then transferred into Part B will be summarized/analyzed only for Part B.

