### 9.3.2. Secondary Efficacy Analyses

The secondary efficacy endpoints for Part A and Part B include the following:

- 28-day all-cause mortality in the ITT Population;
- Clinical cure at TOC in the CRABC m-MITT Population;
- Clinical cure at TOC in the m-MITT, Clinical Evaluable (CE), Microbiologic Evaluable (ME), and CRABC ME Populations;
- Clinical cure at EOT, and LFU in the m-MITT, CRABC m-MITT, CE, ME, and CRABC ME Populations;
- Microbiological favorable assessment at EOT, TOC, and LFU by overall, monomicrobial infection and polymicrobial infection in the m-MITT, CRABC m-MITT, ME, and CRABC ME Populations. Monomicrobial infection is defined as subjects with only ABC pathogens isolated at Baseline, Polymicrobial infection is defined as subjects with both ABC pathogens and non-ABC pathogens isolated at Baseline;
- 14-day all-cause mortality in the CRABC m-MITT and m-MITT Populations; and
- 28-day all-cause mortality in the m-MITT and CRABC ME Populations.

All secondary efficacy analyses will be analyzed including the patients who withdraw consent from the survival status.

In addition, the primary analysis will be repeated for 28-day all-cause mortality in the ITT, m-MITT and CRABC ME Populations excluding the patients who withdraw consent from the survival status for Part A. 14-day all-cause mortality in the CRABC m-MITT and m-MITT Populations will be performed in a same manner excluding the patients who withdraw consent prior to Day 14 for Part A.

Similarly, the analysis of clinical response and the microbiologic response will be repeated excluding patients who withdraw consent from the survival status in the CRABC m-MITT Population for Part A.

The number and percentage of patients in each response category for the secondary efficacy endpoints will be summarized by treatment group. Two-sided 95% CIs computed using a continuity-corrected Z-statistic for the difference in outcome rates between the treatment groups in Part A will be provided. Patients who initially randomized to Part A and transferred to Part B will not be included in Part A analysis and will be included in Part B analysis from the time point of transfer. Patients with a missing secondary efficacy value, the efficacy variable will be considered as non-responder. In addition, time to death will be analyzed using log rank test between the treatment groups for Part A.

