In Part A, if there is a discrepancy between the assessment of the blinded assessor and unblinded Investigator for clinical outcome, the assessment from the blinded assessor will be used. If there is a missing assessment from either the blinded assessor or unblinded Investigator, the other available assessment will be used.

Part B data will be summarized separately from Part A using descriptive statistics. Patients who transfer from Part A to Part B, Part B data will be summarized from the time point of transfer.

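### Part B efficacy pools patients transferred from Part A with direct enrollees, and the SAP does not say where Day 28 starts for the transferred patients

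*SAP*

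**What the plan says.** Transfer can follow randomization to either Part A arm, once Part B is open, "if the ABC identified from the baseline culture is subsequently determined to be resistant to colistin or polymyxin B by the local microbiology laboratory" (SAP 3.1; the Protocol's section 3.1 agrees).

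The efficacy rules for these patients are spread over several sections:

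- **Assignment to a part.** SAP 9.3: "Patients who were randomized into Part A but then transferred into Part B will be summarized/analyzed only for Part B".
- **Start of the Part B data.** SAP 9.3.2 says that they "will not be included in Part A analysis and will be included in Part B analysis from the time point of transfer", and later repeats: "Patients who transfer from Part A to Part B, Part B data will be summarized from the time point of transfer".
- **Baseline.** SAP 9.1.3: "baseline is defined as the last measurement or assessment prior to the first dose of study drug of Part A for Part B efficacy analysis".
- **Study day.** SAP 3.1: "Day 1 is defined as the first day of study drug administration". No separate rule is given for a transferred patient.

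No planned Part B summary separates the two entry routes. SAP 9.3.2 summarizes by treatment group. The Part B definition of the CRABC m-MITT Population in SAP 8.4 does not exclude transferred patients. The subgroup list in SAP 9.3.4 omits transfer status. The one sensitivity analysis that deals with transfers (SAP 9.3.1) restores them to the primary endpoint in the ITT Population and has no Part B counterpart.

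**The concern.** A Part A patient with a resistant isolate who dies before the susceptibility result cannot transfer, so that death never enters Part B. If Day 28 for a transferred patient runs from Part A Day 1, the days before transfer lie inside the 28-day window and cannot contain a death. A direct enrollee has no such protected days.

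Clinical cure is mixed as well. A transferred patient may have spent the first days on colistin or may already have received ETX2514SUL, and is judged against signs recorded before either.

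Efficacy in colistin- or polymyxin B-resistant infection is a named secondary objective (SAP 2.2), and Part B is meant to supplement Part A (SAP 9.1.1). As the SAP stands, two programmers could produce different Part B mortality figures from the same data, and neither table would show how much of the figure comes from transferred patients.

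**Working it through.** **The plan's own figure.** The only stated design figure concerns Part A. With 41% and 36% mortality, a 20-point margin, one-sided 0.025 and 80% power, n per arm = (1.96 + 0.84)² × (0.41×0.59 + 0.36×0.64) / 0.25² ≈ 59.3, rounded up to 60. That gives 120 in total, and 120/0.60 = 200 enrolled. Both figures reproduce, but they do not test this point. The documents state no Part B size, number of transfers or time to transfer.

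**Inputs for an illustration.** Mortality m = 41% is the Part A comparator planning rate (SAP 4), varied from 36% to 50%. Assumed, because the documents give no value: transfer day t = 3 (2 to 5), transferred share of Part B f = 10% to 50%, and hazard shape k = 1 (constant) or 0.5 (strongly front-loaded).

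**Formulas.** Cumulative hazard H(x) = −ln(1−m) × (x/28)^k.

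- Dead before transfer could occur: 1 − exp(−H(t)).
- Day 28 counted from Part A Day 1, given alive at t: 1 − exp(−[H(28) − H(t)]).
- Day 28 counted from transfer: 1 − exp(−[H(28+t) − H(t)]).
- Shift in the pooled Part B rate: f × (conditional rate − m).

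**Transferred patients, m = 41%, t = 3, constant hazard.**

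- Dead before transfer: 1 − 0.59^(3/28) = 5.5%.
- Part A Day 1 clock: 1 − 0.59^(25/28) = 37.6%, which is 41.0 − 37.6 = 3.4 points low.
- Transfer clock: 1 − 0.59^(28/28) = 41.0%, so no shift.

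**Same case, k = 0.5.** The Part A Day 1 clock gives 29.9% and the transfer clock gives 31.8%. What remains under the transfer clock is survivor selection, because patients alive at Day 3 have passed the period of highest risk.

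**Pooled Part B rate, points below 41% (m = 41%, t = 3).**

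| Clock and hazard | f = 10% | f = 25% | f = 50% | Full range (m 36–50%, t 2–5, f 10–50%) |
|---|---|---|---|---|
| Part A Day 1, constant | 0.3 | 0.9 | 1.7 | 0.2 to 3.3 |
| Part A Day 1, k = 0.5 | 1.1 | 2.8 | 5.6 | 0.8 to 8.5 |
| Transfer, constant | 0.0 | 0.0 | 0.0 | 0.0 |
| Transfer, k = 0.5 | 0.9 | 2.3 | 4.6 | 0.7 to 6.6 |

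**What would cancel it.** The hazard ratio in transferred patients that brings their rate back to m is H(28)/[H(28) − H(t)] for the Part A Day 1 clock. At t = 3 with constant hazard this is 28/25 = 1.12. Over t = 2 to 5 and both shapes it runs from 1.08 to 1.73, and from 1.00 to 1.51 for the transfer clock. A larger ratio reverses the direction.

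**The case against.** A reader might infer that Part B mortality is biased low. The documents do not support that as a flat statement, for four reasons.

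1. **The clock is not fixed.** The baseline rule and the general Day 1 definition point to Part A Day 1, but the two sentences on how these patients enter Part B point to transfer. Under a transfer clock and constant hazard the shift is exactly zero.
2. **Direct enrollees are selected too.** Protocol 4.1.3 requires a known susceptibility result for entry by resistance, or at least 48 hours on a polymyxin for entry by failure. This weakens the contrast. It does not remove it, because that survival comes before the direct enrollee's own Day 1 and adds no protected days to the 28-day window.
3. **Other forces act.** Colistin-arm transfers began on a drug to which the local laboratory found their isolate resistant, which could raise later mortality. A hazard ratio of about 1.1 to 1.7 is enough to cancel the effect even under the Part A Day 1 clock.
4. **The share is unknown and may be small.** Known colistin resistance is excluded from Part A (Protocol 4.2, criterion 27), and transfer requires Part B to be open. The 41% is also a Part A rate, while Part B takes urinary and wound infections as well.

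All four stand as limits on direction and size.

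Two further readings also go too far. The early deaths are not lost: a resistant patient who dies before transfer remains in Part A ITT and, if dosed with ABC confirmed from the qualifying culture, in m-MITT. Nor is separation impossible for a reader: SAP 8.4 makes transfer a reason for exclusion from the Part A CRABC m-MITT Population, and SAP 9.2.1 tabulates exclusion reasons and lists them by patient. But listings do not replace a summary. Opposing influences of unknown size are a reason to show the groups apart.

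**Conclusion.** The point holds as a pooling and definition problem. Part B combines patients with different treatment histories and different survival conditions, and the SAP leaves Day 28 undefined for one of the groups.

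If Day 28 runs from Part A Day 1, mortality among transferred patients is understated by about 3.4 points (41% mortality, transfer at Day 3, constant hazard), other things being equal. The pooled figure moves by that amount times the transferred share. Over the assumed ranges the pooled shift runs from 0 to 8.5 points, and the upper end needs a strongly front-loaded hazard and half of Part B to be transfers. If Day 28 runs from transfer, only possible survivor selection remains. The net direction, after allowing for initial ineffective therapy, cannot be settled from the documents.

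The consequence is confined to the reading of Part B. That part is descriptive and carries no test, and the Part A primary analysis already leaves transferred patients out.

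**What to change.** In SAP 9.3 and 9.3.2:

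1. Present Part B 28-day mortality and clinical cure separately for directly enrolled patients and for transferred patients, the latter by original Part A arm. Make direct enrollees the main Part B summary and show the pooled figure alongside.
2. Start the 14- and 28-day mortality clock for transferred patients at the transfer date, and reconcile SAP 9.1.3 with this.
3. Report the number and timing of transfers, and of deaths before transfer among Part A patients with colistin-resistant isolates.
4. Keep the pre-treatment baseline for clinical cure. Cure is defined by signs present at baseline, so resetting it at transfer would redefine the endpoint for patients already partly improved.

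Survival status is recorded at Day 28 or later (SAP 5.4). If a site counts that day from Part A Day 1, a transferred patient may be last seen alive a few days short of 28 days after transfer. Treating such patients as censored in a Kaplan-Meier estimate avoids counting them as missing.

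The cost is SAP wording, a few extra table columns and a smaller main Part B group. No new data are needed.

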### 9.3.3. Exploratory Efficacy Analyses

The following exploratory efficacy endpoints will be summarized by treatment group for the CRABC m-MITT Population for Part A and Part B:

- Clinical cure based on baseline ABC pathogen MIC distribution of ETX2514SUL by overall, monomicrobial infection and polymicrobial infection;
- Clinical cure based on baseline ABC pathogen MIC distribution of colistin by overall, monomicrobial infection and polymicrobial infection;
- Microbiological favorable assessment (including microbiologic eradication and microbiologic presumed eradication) based on baseline ABC pathogen MIC distribution of ETX2514SUL by overall, monomicrobial infection and polymicrobial infection;
- Microbiological favorable assessment (including microbiologic eradication and microbiologic presumed eradication) based on baseline ABC pathogen MIC distribution of colistin by overall, monomicrobial infection and polymicrobial infection;
- Number of days in the intensive care unit (ICU);
- Number of patients transferred to the ICU;
- Number of days on ventilators for patients with VABP, VP, or ventilated HABP, number of days on ventilators;
- Number of days in the hospital;
- Number of days on study drug treatment.

The following exploratory efficacy endpoints will be summarized by treatment group for the m-MITT Population for Part A:

- Clinical cure based on baseline ABC pathogen resistance to ETX2514SUL, carbapenems, or colistin by overall, monomicrobial infection and polymicrobial infection;
- Microbiological favorable assessment (including microbiologic eradication and microbiologic presumed eradication) based on baseline ABC pathogen resistance to ETX2514SUL, carbapenems, or colistin by overall, monomicrobial infection and polymicrobial infection.

Monomicrobial infection is defined as subjects with ABC pathogens only isolated at Baseline. Polymicrobial infection is defined as subjects with both ABC pathogens and non-ABC pathogens isolated at Baseline.

Exploratory endpoints for health resource utilization difference between treatment groups will be reported separately.

### 9.3.4. Subgroup Analyses

The following subgroups based on baseline characteristics will be used for subgroup analyses for the primary efficacy endpoint excluding patients who withdraw consent from the survival status:

- Age group (<65, 65-75 and >75 years)

- Gender (Male and Female)
- BMI (<25, 25-<30, 30-<35, and  $\geq 35$  kg/m^2)
- Charlson comorbidity index (<3 and  $\geq 3$ )
- Diagnosis type (Bacteremia, HABP, VABP, and VP)
- Severity of illness (APACHE II [10-19]/SOFA [7-9]/qSOFA [2] and APACHE II [20-30]/SOFA [ $\geq 10$ ]/qSOFA [3])
- Creatinine clearance group (<30 mL/min, 30-<60 mL/min, 60-<90 mL/min, and  $\geq 90$  mL/min)
- Duration of ICU stay (no ICU stay, <5, 5-14, >14 days)
- HABP/VABP/VP who are identified as positive for ABC by BPP molecular methodology
- Monomicrobial ABC infection vs polymicrobial infection
- Bacteremia patients with negative blood cultures for ABC at randomization or first dose date with a positive blood culture for ABC previously at baseline vs. Rest of bacteremia patients
- Received prior antibiotics within 24 hours prior to the first dose of study drug vs. Not Received
- Received prior antibiotics vs. Not Received
- Septic Shock status at baseline (Yes vs. No)
- Mechanical Ventilation status at baseline (Yes vs. No)
- By region (North America, Europe, Latin America, Asia-Pacific, China; North America/Europe vs. Latin America/Asia-Pacific/China; China vs. rest of the world)
- By COVID-19 status (Positive vs. Negative)

A forest plot will be presented for subgroup analyses.

#### **9.4. Safety Analyses**

All safety summaries and analyses will be performed on the Safety Population. All patients will be summarized based on the actual treatment received. Safety endpoints include the assessment of adverse events and the evaluation of changes from baseline in safety laboratory test results, ECGs, vital signs, and physical examinations.

For each safety endpoint, unless otherwise stated, the last assessment made prior to the first administration of study drug will be used as the baseline value for all analyses.

The safety analyses will be analyzed for Part A and Part B separately. For the patients who were randomized into Part A but then transferred into Part B, safety will be summarized/analyzed until the date of transfer for Part A; safety reported on or after the date of transfer will be summarized/analyzed for Part B. Baseline is the last measurement or assessment prior to the first dose of study drug of Part A for both Part A and Part B safety analysis.

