This is a Phase 3, randomized, active-controlled pivotal study to evaluate the efficacy and safety of IV ETX2514SUL plus imipenem/cilastatin compared to colistin plus imipenem/cilastatin in the treatment of patients with ABC infections. In Part A, all patients will receive imipenem/cilastatin as the best treatment option for HABP, VABP, VP, and/or bacteremia caused by ABC. In addition, the experimental group will receive ETX2514SUL, while the comparator group will receive colistin, both agents targeting drug-resistant ABC. These combinations of drugs should provide all patients with the best treatment options for ABC infections, while anticipating a high rate of drug resistant ABC infections.

Part B will be the open-label, supportive portion of the study that will include patients known to have HABP, VABP, VP, and/or bacteremia infections associated with ABC organisms that are known to be resistant to colistin or polymyxin B, those failing a colistin or polymyxin B regimen prior to study entry or are on acute renal replacement therapy, and patients with infections due to colistin- or polymyxin B-resistant ABC with sources of infection other than HABP, VABP, VP, and/or bacteremia. The goal is to gather preliminary efficacy and safety data in the setting of these other infections and provide a salvage option for XDR strains of ABC infections; hence, Part B will not be pivotal and will not have a comparator. The objective of Part B will be to estimate efficacy of the combination of sulbactam and ETX2514 against colistin- or polymyxin B-resistant ABC infecting various sites, as supporting evidence for Part A results. Safety of ETX2514SUL will be assessed as a whole in Part A and Part B.

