### **2.2 Secondary Objectives**

The secondary objectives of this study are the following:

- To compare the efficacy of ETX2514SUL plus imipenem/cilastatin to colistin plus imipenem/cilastatin in all randomized patients in Part A;
- To evaluate the efficacy of ETX2514SUL plus imipenem/cilastatin in patients with colistin- or polymyxin B-resistant ABC infections in Part B;
- To estimate the efficacy of ETX2514SUL plus imipenem/cilastatin for each primary infection site;
- To evaluate and compare the safety of ETX2514SUL and colistin;
- To describe the overall safety profile of ETX2514SUL; and
- To determine the systemic exposure of ETX2514 and sulbactam in a small cohort of severely ill patients administered ETX2514SUL in Part A.

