#### 9.2.4 Analysis of Safety

All patients who receive any amount of study drug (MITT Population) will be included in the safety analyses. Patients who received the wrong study drug for their entire course of treatment will be analyzed in the group based on the drug received.

A primary analysis of safety will be performed for Part A to assess the proportion of patients with nephrotoxicity, as measured by the RIFLE criteria based on the Safety and CE Populations.

Overall safety will be assessed for Part A and Part B in the Safety Population. The number and percentage of patients in each treatment group reporting at least 1 occurrence of a TEAE for each unique system organ class and preferred term will be tabulated. A TEAE is defined as an adverse event occurring on or after the administration of the first dose of study drug. Treatment-emergent adverse events will also be tabulated by treatment group, severity, and the relationship to study drug as assessed by the Investigator. The number and percentage of patients in each treatment group reporting at least 1 occurrence of a treatment-emergent SAE will be tabulated. The number and percentage of patients (in each treatment group) prematurely discontinuing study drug treatment due to a TEAE will be tabulated by system organ class and preferred term. Adverse events of special interest in Part A will be summarized for all patients by treatment.

Safety laboratory data will be presented by descriptive statistics of the post-baseline value and the change from baseline, as well as the number and percentage of patients with potentially clinically significant laboratory values. Descriptive statistics of vital signs and ECG parameters and the change from baseline will also be presented. An outlier analysis of the ECG parameters will be conducted.

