### 2.2. Secondary Objectives

The secondary objectives of this study are the following:

- To compare the efficacy of ETX2514SUL plus imipenem/cilastatin to colistin plus imipenem/cilastatin in all randomized patients in Part A;
- To evaluate the efficacy of ETX2514SUL plus imipenem/cilastatin in patients with colistin- or polymyxin B-resistant ABC infections in Part B;
- To estimate the efficacy of ETX2514SUL plus imipenem/cilastatin for each primary infection site;
- To evaluate and compare the safety of ETX2514SUL and colistin;
- To describe the overall safety profile of ETX2514SUL; and
- To determine the systemic exposure of ETX2514 and sulbactam in a small cohort of severely ill patients administered ETX2514SUL in Part A.

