**Table 2. Definition of RIFLE Criteria**

Term	Definition
Risk (R)	Increased creatinine level 1.5× or GFR decrease >25%
Injury (I)	Increased creatinine level 2× or GFR decrease >50%
Failure (F)	Increased creatinine level 3×, GFR decrease >75%, or creatinine level ≥4 mg/dL
Loss (L)	Persistent acute renal failure or complete loss of function for >4 weeks
ESKD (E)	ESKD for >3 months

ESKD = end-stage kidney disease; GFR = glomerular filtration rate; RIFLE = Risk–Injury–Failure–Loss–End-stage renal disease.

The number and percentage of patients reporting adverse events of special interest will be summarized by each category and treatment group in Part A in the Safety and CE Populations. In addition, proportion of patients with nephrotoxicity will be compared between the investigational and control groups using Chi-square test. The Chronic hemodialysis patients will not be included in the nephrotoxicity analysis.

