#### 9.4.2. Clinical Laboratory Evaluations

Laboratory test results (hematology, serum chemistry, and urinalysis) at each scheduled visit and change from baseline will be summarized by treatment group for Part A and Part B for Mainland Chinese patients or other patients separately.

Shift tables from baseline to each scheduled post-baseline visit will be provided for selected chemistry parameters (alanine aminotransferase [ALT], aspartate aminotransferase [AST], total bilirubin, creatinine, creatine kinase, alkaline phosphatase [ALP], potassium) and hematology parameters (hematocrit, hemoglobin, platelets, white blood cell count and differential). For chemistry parameters, the following categories will be used: < the lower limit of normal (LLN), normal, > the upper limit of normal (ULN) to ≤3×ULN, >3×ULN to ≤5×ULN, >5×ULN, and missing. For hematology parameters, the following categories will be used: low, normal, high, and missing.

The number and percentage (based on the number of patients with a normal level at baseline) of patients in each treatment group with an ALT (>3×ULN, >5×ULN, and >10×ULN), an AST (>3×ULN, >5×ULN, and >10×ULN), an ALT or AST >3×ULN, and a total bilirubin (>1.5×ULN and >2×ULN) will be presented by study visit. A listing of patients who meet the laboratory criteria for Hy’s law will also be provided. The laboratory criteria for Hy’s law is defined as concurrent ALT or AST>3×ULN, ALP ≤2.0×ULN, and total bilirubin >2×ULN. A listing will also be provided for the potentially clinically significant (PCS) values for the above parameters.

All clinical laboratory data will be listed. Values outside the normal ranges will be flagged.

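### No combined ETX2514SUL safety summary over Parts A and B, and no Part B table of special-interest events (notably RIFLE nephrotoxicity), is planned, although protocol 1.3 and 8.1.4 point to both

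*SAP*

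**What the plan says.** **Combined assessment.** Protocol 1.3 (Rationale) says: "Safety of ETX2514SUL will be assessed as a whole in Part A and Part B". Section 2.2 of both documents lists, apart from the comparison with colistin, the objective "To describe the overall safety profile of ETX2514SUL".

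**How safety is to be analysed.** Protocol 9.2.4 says: "Overall safety will be assessed for Part A and Part B in the Safety Population". It does not say whether the parts are pooled. SAP 9.4 does: "The safety analyses will be analyzed for Part A and Part B separately". No pooled ETX2514SUL summary appears in SAP 9.4 to 9.4.5.

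**Special-interest events.** Protocol 8.1.4 says these events will be summarized in the study report and restricts only the statistical comparisons to Part A. Protocol 9.2.4 is narrower: "Adverse events of special interest in Part A will be summarized for all patients by treatment". SAP 9.4.1, below its Table 2, follows 9.2.4 and applies it to two populations, Safety and CE: "The number and percentage of patients reporting adverse events of special interest will be summarized by each category and treatment group in Part A".

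**Transferred patients.** SAP 9.1.3 includes patients who move from Part A to Part B in both parts for safety. SAP 9.4 splits their data at the transfer date and keeps the baseline before the first Part A dose for both parts. Under protocol 3.1 and 7.7 they may come from either Part A group.

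**The concern.** Protocol 3.1 describes Part A as the first use of ETX2514SUL in intensive care, and the completed Phase 2 study (protocol 1.2) randomized 53 patients to it. Information on uncommon harms is therefore scarce, and every treated patient counts.

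Part B is also a different population. Under protocol 4.1.3 it admits patients with acute kidney injury already on renal replacement therapy, patients who have failed or cannot tolerate a polymyxin, and patients with urinary or wound infections. With separate tables only, and special-interest events tabulated only in Part A, the report would have no single count of patients harmed on ETX2514SUL and no RIFLE incidence in Part B. RIFLE nephrotoxicity is the measure behind a primary objective.

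**Working it through.** **1. Can the reader build the combined summary from the planned tables?** No, for two reasons.
- A patient transferred from Group 1 is in the Part A ETX2514SUL column up to transfer and in Part B afterwards. Adding Group 1 and Group 3 counts that patient twice in the denominator, and twice in the numerator if the same term is reported on both sides of the transfer.
- A patient transferred from Group 2 enters Group 3 after colistin but keeps the pre-colistin baseline. Renal injury begun on colistin would then appear as a change in the ETX2514SUL column.

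A pooled summary therefore needs its own counting and baseline rules. The SAP states none.

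**2. Do other planned outputs supply RIFLE in Part B?** RIFLE (SAP Table 2) grades the fold rise in creatinine (1.5×, 2×, 3×), the GFR decrease, or creatinine of at least 4 mg/dL. The creatinine shift table (SAP 9.4.2) uses fixed bands: below LLN, normal, above ULN to 3×ULN, above 3×ULN to 5×ULN, above 5×ULN.
- The first raised band spans almost a threefold range (3×ULN ÷ ULN = 3). A patient starting between ULN and 1.5×ULN whose creatinine doubles ends between 2×ULN and 3×ULN. That meets the Injury criterion but shows no shift.
- A patient within the normal range at no more than two-thirds of ULN can rise 1.5× and still be normal (2/3 × 1.5 = 1). That meets the Risk criterion but shows no shift.
- Mean change from baseline does not count patients, and the percentage-above-threshold table covers ALT, AST and bilirubin only.
- Adverse event tables count reported terms, not a classification derived from laboratory values.

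The laboratory listings would allow RIFLE to be worked out by hand, but no planned table shows it for Part B.

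**3. How much could pooling add?** The documents state no figure for this, so what follows is an illustration.
- Part A size: 120 ÷ 0.60 = 200, as stated in protocol 9.2.5 and SAP 4. Randomized 1:1, this gives about 200 ÷ 2 = 100 on ETX2514SUL.
- Part B size is not fixed: enrolment runs until Part A completes. I assume 20, 30 or 50.
- Zero-event one-sided 95% upper bound: 1 − 0.05^(1/N).
- Chance of at least one event at a true rate of 1%: 1 − 0.99^N.
- Share of ETX2514SUL patients outside the special-interest table: B ÷ N.

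| Part B patients, B (assumed) | N | Upper bound, no events | Chance of at least 1 event at 1% | Share outside table |
|---|---|---|---|---|
| 0 | 100 | 2.95% | 63.4% | 0% |
| 20 | 120 | 2.47% | 70.1% | 16.7% |
| 30 | 130 | 2.28% | 72.9% | 23.1% |
| 50 | 150 | 1.98% | 77.9% | 33.3% |

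The pooled rows assume a common event rate in the two parts and ignore overlap from transferred patients.

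**The case against.** **The SAP follows the protocol's own analysis section.** A reader might infer that the SAP departs from the protocol by limiting special-interest tables to Part A. It does not: protocol 9.2.4 says the same. The tension is inside the protocol, between 1.3 and 8.1.4 on one side and 9.2.4 on the other. This objection stands.

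**The overall safety objective is met.** A reader might infer that it is not delivered at all. The documents do not support that. The objective is to describe a profile, and the sentence in 1.3 does not define a pooled column. The SAP tabulates adverse events, serious events and discontinuations by treatment group within each part, summarizes laboratory, vital sign and ECG data for both parts, and lists all adverse events. Infections, C. difficile and hypersensitivity terms in Part B would appear in the tables by system organ class and preferred term. This also stands. What remains is the absence of a combined count and of RIFLE in Part B.

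**The laboratory data are not all fragmented.** SAP 9.4.2 says by-visit results and changes "will be summarized by treatment group for Part A and Part B for Mainland Chinese patients or other patients separately". A reader might take this to mean that no all-region laboratory table exists. The split is stated only for those by-visit summaries. The shift tables, the liver threshold table and the Hy's law listing carry no regional split. Protocol 8.6 explains the split: sites in China run all tests locally. No change is needed here.

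**Pooling has its own problems.** Part B is selected, open-label and often exposed to a polymyxin beforehand, and creatinine change is hard to read in patients on renal replacement at entry. This is fair. It means the pooled column must be descriptive and governed by stated rules; it does not justify having no Part B special-interest table.

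**Conclusion.** The point holds in a limited form. Protocol 1.3 and 8.1.4 lead a reader to expect a combined view of ETX2514SUL safety and a special-interest summary not confined to Part A. Protocol 9.2.4 and SAP 9.4 and 9.4.1 provide separate tables, with special-interest events in Part A only. The overall profile is delivered in two parts that cannot simply be added, and RIFLE incidence in Part B appears in no planned table.

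The consequence is modest. The randomized comparison, including the primary nephrotoxicity objective, is untouched. The gain in the zero-event bound, from 2.95% to between 2.47% and 1.98%, rests on an assumed 20 to 50 Part B patients and a common event rate. The stronger reason to act is qualitative: without the added table, no planned output gives RIFLE incidence in Part B, which includes patients with acute kidney injury. The change is worth making before database lock.

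**What to change.** Keep the Part A safety comparison unchanged. In SAP 9.4 and 9.4.1 add:

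1. **A descriptive Part B special-interest table**, including RIFLE. State how patients on acute renal replacement at entry are handled; the SAP's present exclusion from the nephrotoxicity analysis names only chronic hemodialysis patients.
2. **A labelled, non-comparative All ETX2514SUL column** (Group 1 plus Group 3) for treatment-emergent events, serious events, discontinuations and special-interest events. Count each patient once, and count only events from the first ETX2514SUL dose onward. For patients transferred from colistin, either take the last value before the first ETX2514SUL dose as baseline or show them separately. The choice should be explicit: a reset baseline removes injury begun on colistin but may also start from an already raised creatinine.

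Reconcile protocol 1.3 and 8.1.4 with 9.2.4, so that the documents agree on whether safety is pooled and whether special-interest events are summarized in Part B.

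**Cost.** SAP text and table shells. Appendix A of the protocol already schedules daily on-treatment creatinine and adverse event assessment in both parts, so no new data are needed. The downside is that the pooled column mixes randomized with selected open-label patients, so it must be labelled descriptive and not set against colistin.
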